**Table 9.1.6: Schedule of Events – Therapeutic Corticosteroids for ALT Elevations**

	Steroid Treatment Period b								Post-Steroid Period c				
	Week 1	Week 2	Week 3	Week 4	Week 5	Week 6	Week 7	Week 8 b	Week 1	Week 2	Week 3	Week 4	Week 13
Therapeutic corticosteroids (dose in mg/day) a	60 mg	60 mg	40 mg	40 mg	40 mg	30 mg	20 mg	10 mg					
FVIII activity testing									X	X	X	X	
Liver tests									X	X	X	X	
Hepatitis B testing d						X			X				X
HCV Viral Load d						X			X				X

a Therapeutic oral corticosteroids may be initiated according to the parameters set out in Section 9.4.8.2.

b Following initiation or completion of steroid regimen, if a recurrence of ALT values  $\geq 1.5 \times$  ULN or  $>$  ULN and  $> 2x$  baseline value is reported, steroid management decisions will be based on discussions between the Investigator and Medical Monitor. Modification of the steroid regimen may take into consideration possible confounders for the ALT elevation, relationship between increases in ALT and FVIII activity, ALT/FVIII levels post steroid initiation, and adverse events related to steroid dosing. Guidance for tapering oral corticosteroid dosing can be found in Section 9.4.8.2.

c After discontinuation of oral corticosteroids, weekly labs for ALT and FVIII levels will be measured once a week for 4 weeks to ensure stability in values. If these assessments are already being done as part of normal study follow-up, they do not need to be duplicated.

d Should only be performed in subjects with a history of hepatitis B or hepatitis C prior to study entry.

## **9.2 Discussion of Study Design, Including Choice of Control Group**

Study 270-302 is designed to be a Phase 3, single-arm, open-label study in hemophilia A patients with residual FVIII levels  $\leq 1$  IU/dL previously treated with prophylactic exogenous FVIII. Hemophilia A patients who provide written informed consent, meet the entry criteria definition of residual FVIII activity, have well-documented historical data for the previous 12 months concerning exogenous FVIII usage and bleeding episodes, and do not have antibodies to AAV5 will be eligible to enroll in the study.

Approximately 40 subjects will be enrolled at the 4E13 vg/kg BMN 270 dose. Subjects will be followed for 52 weeks post-BMN 270 infusion during which safety and efficacy assessments will be taken. After the final analysis at 52 weeks post-infusion, safety and efficacy will then continue to be assessed long-term for approximately a total of 5 years. During enrollment, the DMC will review available safety and efficacy data on an ongoing basis and may decide to recommend dosing subjects at a different dose level (not to exceed 6E13 vg/kg) based on emerging data from 270-302 and their overall benefit:risk assessment.

Study 270-302 is a self-controlled study. Parameters for each subject will be compared to a pre-treatment assessment of safety (liver function) and efficacy (number of bleeds, use of FVIII replacement therapy).

## **9.3 Selection of Study Population**

Approximately 40 adult hemophilia A patients with residual FVIII levels  $\leq 1$  IU/dL may enroll into the study.

Additional criteria for participation in the study are provided in Section [9.3.1](#) and Section [9.3.2](#).

### **9.3.1 Inclusion Criteria**

Individuals eligible to participate in this study must meet all of the following inclusion criteria:

1. Males  $\geq 18$  years of age with hemophilia A and residual FVIII levels  $\leq 1$  IU/dL as evidenced by medical history, at the time of signing the informed consent.
2. Must have been on prophylactic FVIII replacement therapy for at least 12 months prior to study entry. High-quality, well-documented historical data concerning bleeding episodes and FVIII usage over the previous 12 months must be available.
3. Treated/exposed to FVIII concentrates or cryoprecipitate for a minimum of 150 exposure days (EDs).

4. Willing and able to provide written, signed informed consent after the nature of the study has been explained and prior to any study-related procedures.
5. No previous documented history of a detectable FVIII inhibitor, and results from a Bethesda assay or Bethesda assay with Nijmegen modification of less than 0.6 Bethesda Units (BU) (or less than 1.0 BU for laboratories with a historical lower sensitivity cutoff for inhibitor detection of 1.0 BU) on 2 consecutive occasions at least one week apart within the past 12 months (at least one of which should be tested at the central laboratory).
6. Sexually active participants must agree to use an acceptable method of effective contraception, either double-barrier contraception (ie, condom + diaphragm; or condom or diaphragm + spermicidal gel or foam) or their female partner either using hormonal contraceptives or having an intrauterine device. Participants must agree to contraception use for at least 12 weeks post-infusion; after 12 weeks, subjects may stop contraception use only if they have had 3 consecutive semen samples with no detectable viral vector DNA.
7. Willing to abstain from alcohol consumption for at least the first 52 weeks following BMN 270 infusion.

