
DIAGNOSIS AND ALL CRITERIA FOR INCLUSION AND EXCLUSION: Patients are eligible to be included in the study only if all of the following criteria apply:
 
 
1. Males <math>\geq</math> 18 years of age with hemophilia A and residual FVIII levels <math>\leq</math> 1 IU/dL as evidenced by medical history, at the time of signing the informed consent.
 
2. Must have been on prophylactic FVIII replacement therapy for at least 12 months prior to study entry. High-quality, well-documented historical data concerning bleeding episodes and FVIII usage over the previous 12 months must be available.
 
3. Treated/exposed to FVIII concentrates or cryoprecipitate for a minimum of 150 exposure days (EDs).
 
4. Willing and able to provide written, signed informed consent after the nature of the study has been explained and prior to any study-related procedures.
 
5. No previous documented history of a detectable FVIII inhibitor, and results from a Bethesda assay or Bethesda assay with Nijmegen modification of less than 0.6 Bethesda Units (BU) (or less than 1.0 BU for laboratories with a historical lower sensitivity cutoff for inhibitor detection of 1.0 BU) on 2 consecutive occasions at least one week apart within the past 12 months (at least one of which should be tested at the central laboratory).
 
		

NAME OF COMPANY	SUMMARY TABLE	FOR NATIONAL AUTHORITY USE ONLY:
BioMarin Pharmaceutical Inc. [name]	Referring to Part of the Dossier:  Volume:  Page:	
NAME OF FINISHED PRODUCT: BMN 270		
NAME OF ACTIVE INGREDIENT: AAV5-hFVIII-SQ	Reference:	

6. Sexually active participants must agree to use an acceptable method of effective contraception, either double barrier contraception (ie, condom + diaphragm; or condom or diaphragm + spermicidal gel or foam) or their female partner either using hormonal contraceptives or having an intrauterine device. Participants must agree to contraception use for at least 12 weeks post-infusion; after 12 weeks, subjects may stop contraception use only if they have had 3 consecutive semen samples with no detectable viral vector DNA.
 
7. Willing to abstain from alcohol consumption for at least the first 52 weeks following BMN 270 infusion.
		

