#### **9.7.8.6 Vector Shedding**

During the Post-Infusion Follow-Up period, subjects will undergo testing of various bodily samples to look for evidence of vector shedding for possible viral transmission. Bodily fluids will be tested by polymerase chain reaction (PCR). Fluids tested will include:

- Blood
- Saliva
- Semen
- Urine
- Stool

Vector shedding will also be extensively studied in the present clinical trial, at the time points indicated in [Table 9.1.2](#), [Table 9.1.3](#), [Table 9.1.4](#), and [Table 9.1.5](#). Testing will continue until at least 3 consecutive negative results are obtained. Testing of semen will continue at least through Week 12, even if 3 consecutive negative results have been recorded in that compartment prior to that time point. Subjects who have not had 3 consecutive negative semen samples by Week 52 should continue to have PCR testing in semen every 4 weeks (during Year 2) and every 6 weeks (during Years 3-5) until 3 consecutive negative samples are documented (or upon consultation between the Investigator and Medical Monitor).

Subjects who meet the definition of treatment failure and wish to follow an abbreviated schedule (refer to [Section 12.7](#)) but who have not cleared vector shedding from all fluids must still provide samples for assessment every 4 weeks (during Year 2) or every 6 weeks (during Years 3-5) until vector shedding has cleared. Such subjects may provide samples on the designated study visit dates either at the sites or through use of a MN professional.

Samples may be fractionated prior to shedding analysis in order to better characterize the presence, structure, and location of vector DNA and/or vector capsid within each matrix. If needed, the fractionation may be performed with samples collected specifically for shedding

---

analysis (saliva, blood, semen, urine, feces). Alternatively, the vector DNA characterization during shedding analysis may utilize already fractionated exploratory samples obtained from the above biofluids, such as exploratory plasma samples, exploratory PBMC samples, and red blood cells recovered during PBMC/plasma isolations.

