Fractionation of semen to collect purified sperm separately from non-sperm cells may be performed in parallel at any visit where semen samples are collected. The shedding analysis of a fractionated semen sample will only be performed if vector DNA was detected in the whole semen sample for the same visit. Fractionation of semen during shedding analysis may be stopped if purified sperm tested positive for vector DNA on at least three visits, or if purified sperm tested negative for vector DNA on at least three consecutive visits.

Contraception use may need to be extended beyond 26 weeks in individual subjects based on observed vector shedding in semen. After 26 weeks, subjects may stop contraception use only if they have had 3 consecutive negative semen samples (upon consultation between the Investigator and Medical Monitor).

Details for sample collection and storage are provided in the Laboratory Manual.

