In order to minimize bias and to preserve the scientific and business integrity of the single-arm and open-label study, a data access plan (DAP) was implemented. This document provided guidelines for accessing post-treatment study data and applies to study team members, including personnel from within BioMarin, from external vendors and service providers, from the Data Monitoring Committee (DMC), and from study sites. Role-based access control to study data, both individual patient-level data values as well as aggregated summaries of longitudinal data in an individual patient or across multiple patients, was implemented to minimize potential bias and achieve appropriately controlled decision-making, while preserving operational efficiency. It was enforced by the DAP that individuals who had knowledge of the key efficacy variables (FVIII activity, FVIII usage, and bleeding counts) did not make or influence decisions that would alter the study design or conduct, or the collection or analysis of the key efficacy variables so as to bias the studies’ key efficacy results. The data access control has been lifted from Study 270-302 since September 2019 because only one subject was enrolled in the study and enrollment has been terminated.

In addition, an independent DMC, consisting of experts in clinical trials, statistics, and hemophilia, has been convened in order to assure safe and ethical conduct of the clinical trial. The DMC, supported by an independent statistical service provider, have access to all available data, including both safety and efficacy (e.g., FVIII activity), during the study on an ongoing basis.

An interim analysis was planned after the first approximately 20 HIV-negative subjects have completed the Week 26 visit (or have discontinued study participation prior to Week 26). The concept of the interim analysis was to facilitate initiation of regulatory review of the ongoing study in the event that robust improvements (essentially normalization) in Factor VIII activity in a sufficient proportion

of the population are observed. The interim analysis will not be implemented since enrollment of the study has been terminated since only one subject was enrolled

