8 PROTOCOL DEVIATIONS

The trial's Study Specific Guideline for Managing Protocol Deviations defines protocol deviations, including whether they are minor or major. A data listing of protocol deviations will be provided for ITT population. COVID-19 pandemic related deviations will be flagged in the listing.

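### Inclusion criterion 6 sets a 12-week minimum for contraception, while section 9.7.8.6 works from 26 weeks and adds an unclear consultation clause; the two are not reconciled

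*Protocol*

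**What the plan says.** **Criterion 6.** The eligibility text in protocol section 9.3.1 reads "Participants must agree to contraception use for at least 12 weeks post-infusion; after 12 weeks, subjects may stop contraception use only if" the subject has three consecutive semen samples without detectable vector DNA. The synopsis has the same criterion ("Participants must agree to contraception use for at least 12 weeks post-infusion"). Neither place mentions consultation.

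**Section 9.7.8.6 (Vector Shedding).** Two sentences near the end of the section deal with contraception. The first is "Contraception use may need to be extended beyond 26 weeks in individual subjects based on observed vector shedding in semen". The second is "After 26 weeks, subjects may stop contraception use only if they have had 3 consecutive negative semen samples", and it closes with a parenthesis: "3 consecutive negative semen samples (upon consultation between the Investigator and Medical Monitor").

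**Semen testing rule.** Earlier in the same section, the rule for how long semen PCR continues after Week 52 reads "until 3 consecutive negative samples are documented (or upon consultation between the Investigator and Medical Monitor"). Here the parenthesis contains the word *or*.

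**SAP.** Section 8 states "A data listing of protocol deviations will be provided for ITT population". The SAP synopsis reports that "only one subject was enrolled in the study and enrollment has been terminated".

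**The concern.** The two protocol texts apply the same stopping condition from different weeks. Under criterion 6 the three-sample condition already operates from Week 12, so a separate rule starting after Week 26 would be redundant unless 26 weeks is meant as the ordinary period. The reference to extending use beyond 26 weeks points the same way, although section 9.7.8.6 never states a 26-week minimum.

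The consultation wording adds a second uncertainty. Without a connecting word, the parenthesis can be read as an extra requirement before stopping, as a note on process, or as a slip for the *or* form used for semen testing.

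At stake is consistent instruction on a reproductive precaution in a gene-transfer trial. Criterion 6 is what a participant agrees to at entry; section 9.7.8.6 is where an investigator would look when managing shedding. Whether a stop between Weeks 12 and 26 after three negatives counts as a protocol deviation would depend on which text is applied, unless the study-specific deviation guideline cited in SAP section 8 settles it. That guideline was not available for this review.

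**Working it through.** The plan gives no figure for this difference, so there is none to reproduce. The check compares the texts and then works out the gap from the sampling schedule.

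**Texts side by side**

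| | Synopsis and section 9.3.1, criterion 6 | Section 9.7.8.6 |
|---|---|---|
| Week from which stopping is addressed | 12, stated as a minimum | 26, implied as the ordinary period |
| Sample condition | 3 consecutive negatives | 3 consecutive negatives |
| Consultation | not mentioned | in parenthesis, no connecting word |

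The Amendment 4 summary and the revision table in section 25 change none of these sentences, so this is not a difference from superseded text.

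**Inputs for the gap**
- 12 weeks = 84 days and 26 weeks = 182 days after infusion.
- Semen samples up to Week 8: Day 4 and Day 8 (sections 12.5.2 and 12.5.3), then Weeks 2, 3, 4, 6 and 8 (section 12.5.6), which makes 7. Later samples fall at Weeks 12, 16, 20, 24 and 26.
- Visit window to Week 26: ±48 hours.
- PCR turnaround L: not given in the documents; assumed to be 0 to 28 days.

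**Formula.** With t the day of the third consecutive negative sample, and reading section 9.7.8.6 as a 26-week minimum:

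gap = max(182, t + L) − max(84, t + L)

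**Results**

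| Third negative | t (days) | L (days) | Gap (days) | Gap (weeks) |
|---|---|---|---|---|
| Week 8 or earlier | ≤ 56 | 0 to 28 | 182 − 84 = 98 | 14 |
| Week 12 | 84 | 0 | 182 − 84 = 98 | 14 |
| Week 12 | 84 | 7 | 182 − 91 = 91 | 13 |
| Week 12 | 84 | 14 | 182 − 98 = 84 | 12 |
| Week 12 | 84 | 28 | 182 − 112 = 70 | 10 |
| Week 16 | 112 | 0 | 182 − 112 = 70 | 10 |
| Week 20 | 140 | 0 | 182 − 140 = 42 | 6 |
| Week 24 | 168 | 0 | 182 − 168 = 14 | 2 |
| Week 26 | 182 | 0 | 182 − 182 = 0 | 0 |

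For a third negative at Week 8 there are 84 − 56 = 28 days (26 to 30 with the visit window) for the result to arrive before Week 12. The schedule allows for such early clearance: semen testing must continue through Week 12 even after three negatives. From Week 26 onward only the consultation wording differs.

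**Consultation wording.** The *or* form appears in 7 places: the Table 9.1.5 footnote on PCR testing, section 9.7.8.6, sections 12.6.5, 12.7.1, 12.7.2 and 12.7.3, and SAP section 14.5. The form without *or* appears once, in the contraception sentence of section 9.7.8.6.

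**The case against.** The strongest reply is that the texts do not strictly conflict. Criterion 6 is a commitment made at entry and section 9.7.8.6 is an on-study rule. Both state a necessary condition for stopping, and a subject who follows the later text satisfies both. That is correct, and it makes this an ambiguity and not a hard contradiction. It does not remove the mismatch, because criterion 6 is naturally read as allowing a stop from Week 12.

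The consultation comparison is open to the objection that all seven *or* passages govern how long semen is tested, not when contraception may end, and that silence in criterion 6 contradicts nothing. This stands in part. The comparison shows that the meaning is unclear; it cannot show which meaning was intended, and it is secondary to the difference in weeks.

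The deviation consequence is also uncertain. The deviation guideline is unseen, and the visible schedules contain no assessment of contraception use, so an early stop might not be captured at all. Other safeguards remain: section 9.6 advises against sperm donation while shedding persists, and section 10.4.1.9 requires partner pregnancies to be reported for up to 5 years.

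Semen testing at least through Week 12 lines up with the 12-week figure, but it sets a testing period and does not settle how long contraception is meant to last.

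Finally, the practical reach is very small. The infusion date is not given, but the SAP refers to September 2019 in the past, flags COVID-19 deviations and has visit windows to Week 104. This suggests, without proving it, that the one subject is past Week 26. These points limit the severity; the conflicting instruction remains in the protocol.

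**Conclusion.** The concern holds, as a minor internal inconsistency. The protocol gives two different starting weeks for the same stopping condition, and a consultation clause in only one of the two texts. The nominal difference is at most 14 weeks (98 days). It shrinks with later clearance and is zero from Week 26.

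The size rests on reading section 9.7.8.6 as implying 26 weeks and, where the third negative is at Week 12 or later, on an assumed PCR turnaround. At most one enrolled subject is concerned, and no endpoint, estimate or test is affected.

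Confidence in the wording mismatch is high. The text of protocol section 7.4, the consent form, the Laboratory Manual and the On Site File Binder were not available, and any of them could contain a reconciling statement.

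**What to change.** Reconcile criterion 6 in the synopsis, criterion 6 in section 9.3.1 and the contraception sentences in section 9.7.8.6, so that all three give one minimum duration and one stopping condition. State explicitly whether consultation between the Investigator and Medical Monitor is required in addition to three negative samples or is an alternative to them. Check that the consent form carries the same wording. The sponsor decides which duration and which condition are intended; this review takes no position on that.

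The cost is wording in up to three places and a check of the consent form. No new procedures or data are needed.

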### **9.3.2 Exclusion Criteria**

Individuals who meet any of the following exclusion criteria will not be eligible to participate in the study:

1. Detectable pre-existing antibodies to the AAV5 capsid.
2. Any evidence of active infection or any immunosuppressive disorder, including HIV infection.
3. Significant liver dysfunction with any of the following abnormal laboratory results:
  - ALT (alanine aminotransferase)  $> 1.25 \times$  ULN;
  - AST (aspartate aminotransferase)  $> 1.25 \times$  ULN;
  - GGT (gamma-glutamyltransferase)  $> 1.25 \times$  ULN;
  - Total bilirubin  $> 1.25 \times$  ULN;
  - Alkaline phosphatase  $> 1.25 \times$  ULN; or
  - INR (international normalized ratio)  $\geq 1.4$ .

Subjects whose liver laboratory assessments fall outside of these ranges may undergo repeat testing of the entire liver test panel within the same Screening window and, if eligibility criteria are met on retest, may be enrolled after confirmation by the Medical Monitor.

---

- 4. Prior liver biopsy showing significant fibrosis of 3 or 4 as rated on a scale of 0-4 on the Batts-Ludwig ([Batts 1995](#)) or METAVIR ([Bedossa 1996](#)) scoring systems, or an equivalent grade of fibrosis if an alternative scale is used.
- 5. Evidence of any bleeding disorder not related to hemophilia A.
- 6. Platelet count of < 100 x 10^9/L.
- 7. Creatinine ≥ 1.5 mg/dL.
- 8. Liver cirrhosis of any etiology as assessed by liver ultrasound.
- 9. Chronic or active hepatitis B as evidenced by positive serology testing (HBsAg, HBsAb, and HBcAb) and confirmatory HBV DNA testing. Refer to the Centers for Disease Control (CDC) table for the interpretation of serological test results in the Laboratory Manual.
- 10. Active Hepatitis C as evidenced by detectable HCV RNA or currently on antiviral therapy.
- 11. Active malignancy, except non-melanoma skin cancer.
- 12. History of hepatic malignancy.
- 13. Treatment with any Investigational Product within 30 days or 5 half-lives of the investigational product prior to the screening period. For subjects who have received a prior investigational product, all ongoing adverse events (AEs) experienced while receiving that investigational product must have resolved prior to screening for this study.
- 14. Any condition that, in the opinion of the Investigator or Sponsor would prevent the patient from fully complying with the requirements of the study (including possible corticosteroid treatment outlined in the protocol) and/or would impact or interfere with evaluation and interpretation of subject safety or efficacy result.
- 15. Prior treatment with any vector or gene transfer agent.
- 16. Major surgery planned in the 52-week period following the infusion with BMN 270.
- 17. Use of systemic immunosuppressive agents, not including corticosteroids, or live vaccines within 30 days before the BMN 270 infusion.
- 18. Concurrent enrollment in another clinical study, unless it is an observational (non-interventional) clinical study that does not interfere with the requirements of the current protocol or have the potential to impact the evaluation of efficacy and safety of BMN 270 and with prior consultation with the Medical Monitor.
- 19. Known allergy or hypersensitivity to BMN 270 investigational product formulation.
- 20. Unwilling to receive blood or blood products for treatment of an adverse event and/or a bleeding episode.

